Comparison of Nifedipine Versus Indomethacin for Acute Preterm Labor

NCT03129945

Document Date: 10/17/16

Objective:

Our objective is to compare the prolongation of pregnancy by 48 hours after women are diagnosed with preterm labor prior to 32 weeks gestational age and treated with either nifedipine or indomethacin. We hypothesize that indomethacin will significantly arrest preterm labor by 48 hours in more women compared to nifedipine. The primary outcomes measured will be delaying preterm delivery by 48 hours; secondary outcomes measured will include delay of delivery by 7 days and decreasing delivery before 37 weeks.

Background:

Preterm birth accounts for 70% of neonatal deaths, and 25-50% of cases of long term neurologic impairment in children. About 12% of all live births occur before term and 50% of these were preceded by preterm labor.¹ Tocolytics have been well described in the literature and are recommended to provide time for corticosteroid administration, transfer to a tertiary facility and allow time for magnesium infusion. There are four main categories of tocolytics described by ACOG: calcium channel blockers, prostaglandin inhibitors, magnesium sulfate and B2 agonists. B2 agonists are no longer used outside of an acute setting due to significant maternal side effects; a black box warning has been issued by the US Food and Drug Administration as a result. Magnesium sulfate serves dual purposes in obstetrical medicine: it is used for neonatal neuroprotection and as a tocolytic. However, a recent meta-analysis revealed that it is a weak tocolytic agent compared to other tocolytics. It also revealed that both calcium channel blockers and prostaglandin inhibitors are consistently ranked among the top three tocolytics in delaying delivery by 48 hours, decrease RDS, neonatal mortality and maternal side effects.² The most commonly used and studied tocolytic within the calcium channel blocker class is nifedipine. The most commonly used and studied tocolytic within the prostaglandin inhibitor class is indomethacin. There have been only two published randomized control studies that directly compares nifedipine and indomethacin.^{3,4} These two studies did not have the power or standardization of enrollment to guide us clinically. Here we propose a multi-institutional randomized controlled study directly comparing nifedipine to indomethacin in the setting of preterm labor. We plan to capitalize on the developing network for obstetrical clinical trials within the University of California Fetal Therapy Consortium, and involve all five medical campuses in the state.

Outcomes:

1. To compare the prolongation of pregnancy by 48 hours after women are diagnosed with threatened preterm labor prior to 32 weeks gestational age and treated with either nifedipine or indomethacin. The primary outcome measured will be delay of (preterm

delivery) by 48 hours. Secondary outcomes will be delay of delivery by 7 days and rate of delivery before 37 weeks.

2. Other secondary maternal outcomes included will be maternal adverse side effects significant enough to stop or delay medication use, need for a second tocolytic to halt preterm contractions. Neonatal outcomes measured will be respiratory distress syndrome (RDS), interventricular hemorrhage (IVH), patent ductus arteriosus (PDA), necrotizing enterocolitis (NEC), intubation, number of NICU days and neonatal mortality.

Existing Knowledge:

Specifically we intend to answer the question of which of these two tocolytics should be used as a first line agent. Again there is much evidence showing that calcium channel blockers and prostaglandin inhibitors are the two classes of medications that are superior in delaying delivery for up to 48 hours, decrease RDS, neonatal mortality and maternal side effects compared to other medications.² There has been one poorly designed small study directly comparing nifedipine to indomethacin.³ Another study compared magnesium to nifedipine and to indomethacin. Again, this study had an inadequate sample size. In addition, there was crossover of tocolytic groups, which does not allow for direct comparison. Women in preterm labor typically present with painful contractions and some degree of cervical dilation. There is a small window to treat these patients in an attempt to arrest preterm labor. Using the optimal tocolytic agent initially can potentially prevent or delay preterm birth with its resultant neonatal morbidity and mortality.

Previous Research:

Nifedipine is a well-studied tocolytic. A Cochrane review in 2011 evaluated data on all calcium channel blockers used for tocolysis; over 1029 women were included in the review. When compared to other tocolytic agents, calcium channel blockers decrease delivery within 7 days, decrease delivery less than 34 weeks, and have less need to stop medication for maternal adverse effect. Furthermore calcium channel blockers (compared to other tocolytics) decreased the incidence of RDS, NEC, IVH and neonatal jaundice in the newborn.⁵ Nifedipine has thus shown benefit as a tocolytic. One meta-analysis demonstrated that nifedipine compared to B2 agonists had a reduction of preterm labor within 7 days, delivery before 34 weeks and reduction of RDS, NEC, IVH, neonatal jaundice, admission to the NICU and NICU stay. Compared to magnesium, nifedipine was associated with fewer maternal side effects. Although no difference in major neonatal outcomes were demonstrated, there was a significant decrease in NICU admission and NICU length of stay with nifedipine.⁶

Indomethacin has also been well studied. The Cochrane review looked at COX inhibitors and their use as a tocolytic. Of the 13 trials included, 10 specifically used

indomethacin. When compared to placebo, there was reduction in birth before 37 weeks gestation, an increase in gestational age at time of delivery and increase in birth weight. When compared to other tocolytics there was a reduction in birth before 37 weeks as well as reduction in maternal drug reaction.⁷

There have been two large meta-analyses comparing tocolytics to determine the optimal first line agent. The first was published in 2009 to compare the outcomes of delaying delivery at 48 hours, 7 days and until 37 weeks. A decision tree was created using the highest efficacy to toxicity ratio. The study concluded that all tocolytics were superior to placebo for delaying delivery for 48 hours and 7 days. In addition, prostaglandin inhibitors were superior to other tocolytic agents.⁸ As described above, the second open network meta-analysis reviewed all tocolytics to determine the best probability for delaying delivery by 48 hours, and to decrease RDS, neonatal mortality and maternal side effects. Both prostaglandin inhibitors and calcium channel blockers were ranked among the top three medication classes for each category. Specifically prostaglandin inhibitors were ranked the best tocolytic in delaying preterm delivery within 48 hours and maternal side effect.

Calcium channel blockers ranked the best tocolytic for neonatal outcomes.² As discussed above, there have been two randomized control studies comparing nifedipine versus indomethacin. The first study included a total of 79 patients comparing nifedipine to indomethacin. This study found that nifedipine was superior for arresting contractions during the first two hours; however, if there was a response to indomethacin within the first two hours, there was no difference in delivery at 48 hours or up to 7 days. There are several design flaws in the study including the small sample size for which a calculation was not described, use of dosing regimens for both nifedipine and indomethacin that are not commonly used, and generous, non-standard inclusion criteria for preterm labor.³

The second randomized control study compared 3 different tocolytics: nifedipine, indomethacin and magnesium. This study had several flaws as well, including a small sample size (approximately 90-114 in each group) and tocolytic group cross over. Although tocolytic cross over was allowed, the subjects remained in their initial group for analysis and for this reason this study does not allow for direct comparison. In addition, twin gestations were included. This group is at high risk for preterm delivery and neonatal morbidity at baseline, are thought to have a different mechanism for preterm delivery, and likely have a different response to tocolytic agents, all of which could potentially skew data. They also reported a gestational age of enrollment from 20 to 32 weeks. As the main goal of tocolytic therapy is to administer corticosteroids (given between 24-34 weeks gestation) and allow transfer to a tertiary center, inclusion of patients less than 23 weeks gestation – who fall within the non-viable range and typically are not considered candidates for intervention, with tocolytic treatment or corticosteroid administration, was problematic in this study.⁴

This proposed study will be a multi-institutional study to directly compare the two tocolytics that have been shown to be superior in meta-analysis. Determining a first line treatment will help guide clinicians in the treatment of preterm labor.

1. Management of preterm labor. Practice bulletin No. 127. American College of Obstetricians and Gynecologists. *Obstet Gynecol* 2012; 119: 1308-17.

Methods:

This is a randomized controlled open-label trial comparing two groups of women with preterm labor who are treated with either indomethacin or nifedipine as a tocolytic agent. The study will be conducted at each of the five University of California medical center hospitals. In order to be admitted to the hospital for tocolytic treatment, subjects will have to be in preterm labor defined as regular uterine contractions (at least 6 per hour) associated with changes in cervical dilatation and/or effacement, cervical dilatation of > 2 cm at presentation or a change in cervical dilatation of > 1 cm, and > 25 to 50% effacement and/or a short cervical length (per institution's policy) as obtained by transvaginal cervical sonography with or without a positive fetal fibronectin. All women will be treated in a uniform fashion with initial hydration, evaluation for etiologic infection, administration of antenatal corticosteroids to accelerate fetal maturity, and magnesium sulfate for neuroprotection. Magnesium will be administered according to each institution's magnesium for neuroprotection protocol. Women will be randomized to either tocolytic therapy with nifedipine or indomethacin by using computerized randomized block sequencing.

Nifedipine Treatment: Subjects will be given nifedipine 10mg orally and repeated every 20 minutes for a maximum dose of 30mg in the first hour followed by 20mg every 6 hours for the first 48 hours of treatment. This is a commonly used dose and has been described in a large meta-analysis reviewing nifedipine in the management of preterm labor by Conde-Agudelo et al.¹ Of the 26 studies reporting on nifedipine as an acute tocolytic, the dosing ranged from a loading dose of 10 to 30mg orally or sublingually, followed by 10 to 20mg orally every 4-8 hours. 12 of those studies used a repeat loading dose every 15-20 minutes. The decision was made to proceed with nifedipine 10mg orally and repeated every 20 minutes for a maximum dose of 30mg followed by 20mg every 6 hours since it is a commonly prescribed dosing for acute tocolysis.

Indomethacin Treatment: Those randomized to indomethacin will be given 100mg orally as a loading dose followed by 50mg every 6 hours for the first 48 hours of treatment. This regimen was decided after reviewing the Cochrane review on COX inhibitors for treating preterm labor.² 10 of the 13 trials included in the review used indomethacin. The dosing ranged from 50 to 100mg loading dose followed by 25mg to 50mg orally every 4-6 hours. The loading dose was mostly given rectally. A recent randomized control trial compared indomethacin vs. two other tocolytics.³ The indomethacin dosing used was an initial 100mg suppository, repeated one time if contractions persisted after two hours, followed by 50mg orally every 6 hours. This regimen was associated with increased incidence of fetal ductal constriction (13/97) and oligohydramnios (5/97) when compared to the other two treatment groups. Therefore, we propose using a one time loading dose of 100mg orally followed by 50mg every 6 hours, which is a commonly prescribed dosing. Using the lower end of the normally prescribed dosing range should have decrease fetal and maternal side effects.

Tocolytic failure will be defined as delivery within 48 hours of initiation or the start of magnesium for neuroprotection. Magnesium for neuroprotection is started when delivery is deemed imminent, so when initiated, it is implied that there has been tocolytic treatment failure. That being said, it is difficult to predict preterm birth, especially in the setting of preterm labor, and some clinicians may start magnesium for neuroprotection without labor proceeding to delivery. There is a theoretical risk of neuromuscular blockade with the concurrent use of magnesium and nifedipine, and there have been 2 case reports of reversible neuromuscular blockade in this setting.^{4,5} One of these case reports used a total dose of 500mg of magnesium⁵ – which is significantly more than what would be administered for our neuroprotective dosing. There are studies, albeit small, that show concurrent use of nifedipine and magnesium is safe in the setting of preeclampsia.^{6,7,8} One such study describes expected hemodynamic changes with the concurrent use of nifedipine and magnesium including a decreased mean arterial pressure, systemic vascular resistance and increase in cardiac index.⁷ The magnesium dosing in the study was 5 grams over 20min followed by 3g/hr which is a higher maintenance dose than any of the campuses uses for neuroprotection.

One of the largest studies that examined maternal and neonatal outcomes in the setting of preeclampsia was the Magpie trial,⁸ which had about 30% concurrent use with nifedipine and magnesium with no adverse effects reported. While on magnesium, all 5 campuses have mechanisms in place to monitor closely for magnesium toxicity including serial neurologic exams and/or magnesium levels. If any early adverse signs are seen, magnesium will be discontinued and/or calcium gluconate administered to reverse any neuromuscular blockade. For this reason, concomitant use of magnesium with either nifedipine or indomethacin is left to the judgment of the providers at each institution.

After 48 hours from the first dose of antenatal corticosteroids, the tocolytic agent will be discontinued. Maintenance tocolysis for longer than 48 hours will not be used on study patients. The study time required from each subject is the duration of hospital admission during which she is enrolled in the study and the duration of the birth hospitalization for each infant. To clarify, secondary outcomes measured will include delay of delivery by 7 days and decreasing delivery before 37 weeks as outlined in section 1 on page 2. Section 3 specifically asks the time required by study participants. Gestational age at delivery is an endpoint we plan to collect and the end of the study participants' time in the study. Gestational age at delivery will be collected as data but analyzed in a dichotomous fashion i.e. prior to 37 weeks. End points for tocolytic treatment are arrest of preterm labor (cervical dilation) or completion of betamethasone administration (e.g. 48 hours from the first dose). The primary study outcome is extension of pregnancy by 48 hours after admission. The secondary outcome is gestational age at delivery. We will also evaluate pregnancy extension by 7 days after treatment initiation. It is likely that some patients are discharged still pregnant and return later in gestation for delivery. Although no actual study time between these two time points are required of the subject or during subsequent hospitalization(s), data would be collected at the time of delivery.

For the neonates, data will be collected through discharge. No neonatal follow up is required. There may be subjects who deliver at another hospital. If the patient gives permission, then we will obtain records from the appropriate hospital.

Subject's privacy will be protected by using HIPPA guidelines by limiting access to data collection study personnel only. In addition, data will always be kept in a secured, locked location. Subject screening, enrollment and case report forms will be kept in a binder that will be locked in a room/drawer at all times. These case report forms will be uploaded to a secure online database run by a well-established company Tiatros. Tiatros uses online software to organize, analysis and allow communication among principal investigators in the study. Most importantly this is done securely and follows HIPPA regulations.

Summary

This comparative study of nifedipine versus indomethacin for acute preterm labor will be conducted at the 5 UC medical campuses (UC Irvine, UC Davis, UC San Diego, UC San Francisco, UC Los Angeles) using the Reliance Agreement. UCI is the reviewing IRB. UC Davis, UCSD, UCSF, UCLA are the relying IRBs. All tocolytic treatment will be given in the primary hospital at each campus. Medication is discontinued once there is arrest of preterm labor, 48 hours from first dose of betamethasone, or when delivery is deemed imminent or unavoidable, and depending on institution's policy at the time magnesium initiated for neuroprotection. No maintenance tocolytic medication will be given (i.e. longer than 48 hours) and none will be given as an outpatient.


Statistical Analysis:

The purpose of this study is to determine whether nifedipine or indomethacin is superior in arresting preterm delivery by 48 hours. We expect the nifedipine group to arrest preterm labor for 48 hours in 72% of cases¹ and the indomethacin group to arrest preterm labor for 48 hours 83% of cases.² Using a power of 80%, alpha of 0.05 we calculate 225 subjects are needed in each group.

The primary outcomes and other dichotomous outcomes will be evaluated using Chi-square. We also anticipate a 25% difference between groups based on prolongation of pregnancy by one week based on a small RCT using nifedipine vs. ritodrine conducted by Papatsonis et al.³ Continuous variables will be compared using Student's t-test. Sub-group analyses will be done to compare differences across the sites. Regression analyses will be applied where appropriate such as for neonatal complications and the consideration of gestational age.

3. Papatsonis et al. Nifedipine and ritodrine in the management of preterm labor: a randomized multicenter trial. *Obstet Gynecol* 1997; 90:230-4.

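### The only maternal side-effect outcome is triggered by stopping or delaying medication, which gives early transient effects more opportunity to be counted on nifedipine than on indomethacin

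*Combined protocol and SAP*

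**What the plan says.** Item 2 of the Outcomes section lists one maternal tolerability outcome: "maternal adverse side effects significant enough to stop or delay medication use". It gives no severity grade, assessment time or window. The other maternal item there, need for a second tocolytic, concerns efficacy.

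The schedules are in Methods. The Nifedipine Treatment paragraph specifies "nifedipine 10mg orally and repeated every 20 minutes for a maximum dose of 30mg in the first hour followed by 20mg every 6 hours". The Indomethacin Treatment paragraph specifies "100mg orally as a loading dose followed by 50mg every 6 hours", and later calls the load a single one: "we propose using a one time loading dose of 100mg orally followed by 50mg every 6 hours".

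Methods describes the trial as open-label. The Summary lists when study medication ends: "Medication is discontinued once there is arrest of preterm labor, 48 hours from first dose of betamethasone, or when delivery is deemed imminent or unavoidable". The start of magnesium is a further reason there, subject to local policy. Maternal intolerance is not in that list, so the documents give no criterion for the event that the outcome counts. Under Statistical Analysis, "The primary outcomes and other dichotomous outcomes will be evaluated using Chi-square".

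**The concern.** A delay can be observed only if there is a dose to delay. During loading, the nifedipine arm has repeat doses that may be due and the indomethacin arm has nothing due until the six-hourly doses begin. Take the same symptom, of the same severity, starting 15 minutes after the first dose and gone within a few hours. On nifedipine it may hold back a second or third loading dose and so become an event. On indomethacin there is no dose to hold, and it becomes an event only if the provider decides to stop treatment.

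Two equally tolerated drugs could then show different event rates because of their dosing calendars, and a plain chi-square comparison cannot separate the calendar from the drug. The decision to hold a dose is also taken by staff who know the treatment and have no stated criteria. The trial aims to identify a first-line agent, and its background sections cite maternal side effects as one ground for choosing between tocolytics, so a reader is likely to use this comparison.

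**Working it through.** **1. The plan's own figure.** The design inputs are 72% and 83% success, power 80% and alpha 0.05 (Statistical Analysis).

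- Two-sided, pooled variance under the null: n = [1.960·√(2·0.775·0.225) + 0.842·√(0.72·0.28 + 0.83·0.17)]² / 0.11² = 225.04, which rounds up to 226.
- Unpooled variance gives 223 and the arcsine method 224. Power at 225 per group is 0.800.

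The stated 225 is reproduced. It concerns the primary outcome, and nothing below alters it. It is used here only as the arm size.

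**2. Count of doses that could be held after the first dose.** Nifedipine loading doses are taken at 0, 20 and 40 minutes (three doses of 10 mg reach the 30 mg maximum), and the indomethacin load at 0. The documents do not time the first six-hourly dose exactly. I place it at hour 6 in both arms, with the last at hour 42.

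| Window after first dose | Nifedipine | Indomethacin |
|---|---|---|
| First hour | up to 2 | 0 |
| Before hour 6 | up to 2 | 0 |
| Before hour 48 | up to 2 + 7 = 9 | 7 |

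The whole difference lies before hour 6. After that the arms have the same number of doses.

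**3. Consequence on assumed rates.** The documents give no side-effect rates, so every rate here is an assumption. Let both drugs be equally tolerated, with:

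- r = 3% of each arm having a later stop or delay;
- e = 2%, 5% or 7.5% of each arm having, in addition, an early transient effect of the kind that would hold a dose if one were due;
- f_N and f_I the fractions of those early effects actually recorded in the nifedipine and indomethacin arms.

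The recorded proportions are p_N = r + f_N·e and p_I = r + f_I·e. For example, with e = 5%, f_N = 1 and f_I = 0, p_N = 0.03 + 0.05 = 8% against 3%, or an expected 225 × 0.08 = 18 events against 225 × 0.03 = 6.75.

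The table shows how often a two-sided 5% chi-square without continuity correction declares a difference at 225 per arm:

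| Recorded f_N / f_I | e = 2% | e = 5% | e = 7.5% |
|---|---|---|---|
| all / none | 5% v 3%: 19% | 8% v 3%: 65% | 10.5% v 3%: 91% |
| half / none | 4% v 3%: 9% | 5.5% v 3%: 26% | 6.75% v 3%: 46% |
| quarter / none | 3.5% v 3%: 6% | 4.25% v 3%: 11% | 4.875% v 3%: 17% |
| half / quarter | 4% v 3.5%: 6% | 5.5% v 4.25%: 9% | 6.75% v 4.875%: 13% |

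With equal recording (3% v 3%) the test rejects 5% of the time, so the excess comes from unequal recording alone. The result depends at least as much on f_N and f_I as on e.

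**The case against.** A reader might infer that the same early side effect counts in one arm only. The documents do not support that, for three reasons.

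- The outcome refers to stopping or delaying medication use, not a dose. A decision at 15 minutes to stop indomethacin counts although nothing is due, and so does an effect that lasts until the next dose.
- The 30 mg of nifedipine is a maximum, and the text does not say whether the repeats are fixed or depend on response. Some women may have no second or third dose to hold.
- The documents give no data on how often such effects occur or how soon they appear.

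These points remove the absolute reading and make the all/none row an upper case. They do not remove the difference in opportunity.

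A second objection is that stop/delay is a deliberate, pragmatic endpoint. The protocol's Previous Research section itself reports stopping for maternal adverse effects from a review of calcium channel blockers. If split loading leads to more interruption, that is a real property of the regimen. This stands: stop/delay is a legitimate measure of regimen tolerability and should be kept. But as the only maternal side-effect outcome, it cannot show whether a difference reflects more or worse symptoms or merely more chances to interrupt.

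A reader might also infer that the asymmetry favours the trial's hypothesis. The hypothesis under Objective concerns delay of delivery by 48 hours only. The asymmetry works against nifedipine on tolerability and says nothing about that hypothesis.

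**Conclusion.** The point holds in a limited form. For early effects that settle before hour 6 without treatment being stopped, dose interruption is an unequal marker of severity, with up to two doses that could be held on nifedipine against none on indomethacin. The direction is against nifedipine. Open-label decisions without criteria add uncertainty to what is recorded.

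The size is unknown. Under the assumed rates, the chance of a false difference runs from 6%, barely above nominal, to 91% in the extreme all/none case. That range shows sensitivity and is not an estimate for this trial. It rests on equal true tolerability, a 3% later rate in each arm, 225 per arm and the stated recording fractions.

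Only one secondary outcome is affected. The change is worth making because it is cheap, but the point does not call into question the primary comparison or the sample size.

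**What to change.** In item 2 of Outcomes, base the between-arm comparison of maternal tolerability on maternal adverse effects that meet one stated severity definition. Record them over the same window from first dose in both arms, whether or not a dose was due or changed.

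Keep stop/delay as a separate regimen-tolerability item, with the time and reason for each event, and report it separately before and after hour 6.

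The cost is a sentence or two in the outcome list and a case-report-form item. Side-effect recording increases slightly, and the new outcome will be commoner than the stop/delay version. No change to dosing or sample size is needed.

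### A fetal death after randomisation enters no planned harm comparison, and under the delivery-only outcome wording it can count as a success

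*Combined protocol and SAP*

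**What the plan says.** Outcomes, item 2, lists two further maternal outcomes: need for a second tocolytic, and "maternal adverse side effects significant enough to stop or delay medication use". The offspring outcomes are RDS, IVH, PDA, NEC, intubation and, to close the list, "number of NICU days and neonatal mortality". The Methods add: "For the neonates, data will be collected through discharge".

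The primary outcome is a delay of delivery by 48 hours in the Objective and in Outcomes, item 1. The Methods put it this way: "The primary study outcome is extension of pregnancy by 48 hours after admission". Delay by 7 days is a secondary outcome. None of these requires the fetus to be alive.

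The Methods also define failure: "Tocolytic failure will be defined as delivery within 48 hours of initiation or the start of magnesium for neuroprotection". Earlier in the Methods, the sentence beginning "All women will be treated in a uniform fashion with initial hydration, evaluation for etiologic infection, administration of antenatal corticosteroids" goes on to include magnesium for neuroprotection in the treatment that all women receive.

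Stillbirth, intrauterine death and perinatal mortality appear nowhere as an outcome, a failure event or an analysis rule. The denominator for the neonatal outcomes is not stated.

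**The concern.** Delaying delivery is worth having because it may improve the infant's outcome; the Existing Knowledge section says as much when it sets out to choose the first-line agent. If the fetus dies while the woman remains undelivered, the delay has no such value. Yet the delivery-only outcomes give full credit for it, and the mortality outcome does not register the loss.

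The maternal side-effect item does not fill the gap. Fetal death is not a maternal side effect, and because treatment ends by 48 hours from the first steroid dose, a later death could not stop or delay medication. The plan has no general adverse-event outcome that would compare such events between arms.

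The protocol treats fetal effects as relevant to one of the drugs. In an earlier trial's indomethacin arm it reports constriction of the fetal ductus in 13 of 97 and oligohydramnios in 5 of 97, and it gives side effects as a reason for its own regimen. It plans no fetal outcome.

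**Working it through.** **1. Arm size.** Inputs from Statistical Analysis: 72% v 83%, power 80%, alpha 0.05 (sidedness not stated; taken as two-sided). With mean proportion 0.775:

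n = [1.960 × √(2 × 0.775 × 0.225) + 0.842 × √(0.72 × 0.28 + 0.83 × 0.17)]² / 0.11² = (1.157 + 0.493)² / 0.0121 ≈ 225 before rounding (226 when rounded up).

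The plan's 225 per group is reproduced, with power 80.0% at 225. It is not in dispute, and it supplies the denominator used below.

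**2. How the text scores a fetal death.**

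| Situation | Delivery-only wording | Failure definition in Methods | Neonatal mortality |
|---|---|---|---|
| Died by 48 h, undelivered at 48 h, magnesium not started | Success | Not a failure | Not counted |
| Died by 48 h, undelivered at 48 h, magnesium started | Success | Failure | Not counted |
| Died and delivered within 48 h | Failure | Failure | Not counted |
| Died by 7 days, undelivered at 7 days | Success at 7 days | No 7-day rule | Not counted |
| Died later, before delivery | Earlier success stands | Not affected by the death | Not counted |

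The last column is the same in every row. The second row shows the two definitions of the 48-hour result disagreeing, for a reason unrelated to the fetus.

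**3. Effect on the primary proportion.** One case per arm is 1/225 = 0.44 percentage points.

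**4. Effect on the mortality comparison (illustration).** Assume one fetus per woman and 3% neonatal death in each arm: 0.03 × 225 = 6.75, about 7. Assume further that 1 to 5 fetal deaths occur in one arm and none in the other. The planned outcome shows 7 v 7 throughout.

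- 1 fetal death: 8 v 7, ratio 8/7 = 1.14
- 3 fetal deaths: 10 v 7, ratio 10/7 = 1.43 (95% CI 0.55 to 3.69, chi-square p = 0.46)
- 5 fetal deaths: 12 v 7, ratio 12/7 = 1.71 (p = 0.24)

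**5. Would a rule be needed?** For an assumed fetal death rate f, the expected count per arm is 225f and the chance of at least one among 450 women is 1 − (1 − f)^450.

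| f (assumed) | Expected per arm | Chance of at least one in 450 |
|---|---|---|
| 0.2% | 0.45 | 59% |
| 0.5% | 1.1 | 90% |
| 1% | 2.3 | 99% |
| 2% | 4.5 | over 99.9% |

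**6. Power if such cases are rescored.** Suppose every case occurs by 48 hours, is undelivered, and sits inside the planned 72% and 83%. If the rate is equal in both arms, power at 225 per arm is 79.4% (f = 0.5%), 78.8% (1%) and 77.6% (2%). If all cases are in the indomethacin arm, it is 75.9%, 71.4% and 61.5%. The last figure needs 2% fetal death within 48 hours in one arm only, which nothing in the documents suggests.

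**The case against.** The other side can make a good case.

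- **The failure definition already catches some cases.** A woman given magnesium for neuroprotection is a failure whatever happens to the fetus. This stands as a qualification, so a reader should not infer that every undelivered fetal death scores as a success. It does not close the gap: the clause is not about fetal death, does not extend to 7 days, and conflicts with magnesium as uniform treatment and with the delivery-only primary outcome.
- **Efficacy is not necessarily inflated.** A reader might infer that a fetal death improves the efficacy result. It does so only where it takes the place of an early delivery. If the woman would have been undelivered anyway, her score is unchanged, and if she delivers within 48 hours she is a failure.
- **No drug is shown to cause fetal death.** The cited findings are ductal constriction and oligohydramnios, not deaths, under a regimen with a possible repeat loading dose that this protocol departs from. A reader might infer a known excess of deaths; the documents do not support that.
- **The trial could not resolve the difference.** This also stands: 10 v 7 gives p = 0.46. It limits what could be concluded from the counts, but is no reason to leave them out of the comparison.
- **Rescoring could contaminate a short-term outcome.** If any later stillbirth reversed a 48-hour success, the primary outcome could not be settled at 48 hours and would depend on later records. This is a fair warning, and the rule must be limited to each time point.

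**Conclusion.** The concern holds as a gap in the outcome definitions, and it should be closed. Two things follow from the text without any assumed rate: fetal death is in no planned harm comparison, and the delivery-only wording can credit it as a success at 48 hours or 7 days.

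The effect on the primary outcome is minor, and the sample size is unaffected as a calculation. What is lost is a complete count of deaths by arm. The ratios of 1.14 to 1.71 rest on an assumed 3% neonatal death rate and on extra deaths in one arm only, so they show the mechanism and predict nothing.

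A reader might also infer that the plan specifies live-born infants as the denominator for the neonatal outcomes. It states no denominator. The narrower point is that the listed outcomes are defined for neonates, so a fetus that dies before birth has no place in them.

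**What to change.** 1. In Outcomes, item 2, replace neonatal mortality with: *perinatal death: fetal death after randomisation, or infant death before hospital discharge*. Put every fetus of a randomised woman in the denominator and show the two components separately by arm.
2. For the 48-hour and 7-day outcomes, count a woman as not a success if fetal death has occurred by that time point, and only then. A later stillbirth does not reverse an earlier success and is reported under perinatal death.
3. Reconcile the three Methods statements on magnesium as uniform treatment, magnesium as failure, and the delivery-only primary outcome, so that each woman has one 48-hour result.

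Because the trial is open-label, these rules should be fixed before outcome data are seen.

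The cost is mainly wording, since the Methods already provide for data collection at delivery. Success proportions may fall by a fraction of a point. Perinatal death will be missing for some women who deliver at another hospital and do not permit access to records, a limit that neonatal mortality already has. The 48-hour result does not wait for delivery records, because the rule stops at the time point.
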